The study participants are at minimal risk for harm as a result of participation in the proposed research study. Although unlikely, one risk of the proposed study is that participants will experience emotional discomfort as a result of completing the survey or interview questions. These questions might cause the participant temporary embarrassment, worry, anxiety, or depressed mood. Breach of participants' confidentiality presents another possible risk. Such a breach could cause damage to one's

reputation and associated mental distress. The investigative team's strategies to protect against both risks are described below.

2. **Minimizing Risks:** Describe the manner in which the above-mentioned risks will be minimized. Protection Against Risk:

Protection Against Emotional Discomfort: It is possible that participants may experience emotional discomfort in responding to the self-report measures. While every possible step will be taken to minimize such risk, consent documentation will make it clear that, if participants have any concerns about any aspect of the study, they may refuse to continue with the study at any time without penalty. In addition, we will remind participants during the course of their assessments that they can refuse to answer any questions and may discontinue participation at any time. Clinical staff members at the Esteem Research Program are thoroughly trained in appropriate responses to participant distress through regular trainings by this study's Yale University PI, [name]., a licensed clinical psychologist. This training addresses the appropriate handling of imminent threats and provision of referrals to free counseling services in less imminent clinical situations. A designated staff member with an advanced degree in a mental health profession is always on site to enact the Clinical Protocol. The Clinical Protocol clearly outlines procedures for assessing participant emotional distress and referring participants to appropriate care resources.

Protection Against Breach of Confidentiality: The primary potential risk to participants is breach of confidentiality. Breaches of confidentiality will occur if a participant reports a clear intention to harm himself or another person. Additionally, health care professionals are required by state law to report suspected cases of abuse or neglect. The likelihood that any additional breaches of confidentiality would occur is minimal, as steps will be taken to guard against this risk. All the Esteem Research Program counselors and research assistants (RAs) have undergone rigorous training in maintaining participants' privacy and confidentiality. Further, immediately upon providing consent, all participants will be assigned an identification number, which will only be kept on an electronic database that will be password protected and located on a designated the Esteem Research Program computer. This information will not be stored with any other data and no other identifying information will appear on any form. All contact with participants will be made by counselors and research staff under explicit guidelines to preserve confidentiality when telephoning, emailing, or mailing information to participants. All materials with identifying information will be kept in one password protected electronic file. Participants will provide the Esteem Research Program with alternative contact information (email, phone numbers, and mailing address) for compensation and study retention purposes. This information will be treated in the same confidential manner as all participant information, as described here.

- 3. **Data and Safety Monitoring Plan:** Include an appropriate Data and Safety Monitoring Plan (DSMP) based on the investigator's risk assessment stated below. (Note: the HSC will make the final determination of the risk to subjects.).
 - a. What is your assessment of the overall risk level for subjects participating in this study? This study proposes to ask participants a series of questions assessing their life experiences as gay, bisexual, or other women who have sex with women. Empirical data suggest that answering questions regarding sex and mental health is associated with minimal risk.¹ 'Yeater, E., Miller, G., Rinehart, J., & Nason, E. (2012). Trauma and sex surveys meet minimal risk standards: implications for institutional review boards. Psychol Sci, 23(7), 780-787. doi:10.1177/0956797611435131

- b. If children are involved, what is your assessment of the overall risk level for the children participating in this study? N/A
- c. Include an appropriate Data and Safety Monitoring Plan. Examples of DSMPs are available here http://your.yale.edu/policies-procedures/other/data-and-safety-monitoring-plan-template for

i.Minimal risk

ii.Greater than minimal/moderate risk

We consider our study as minimal risk. The principal investigator and the research assistants are responsible for monitoring the data, assuring protocol compliance, and conducting the safety reviews daily. During the review process, the principal investigator will evaluate whether the study should continue unchanged, require modification/amendment, or be closed to enrollment. The principal investigator, the Institutional Review Board (IRB), and Yale School of Public Health (YSPH) have the authority to stop or suspend the study or require modifications. This protocol presents minimal risks to the subjects and Unanticipated Problems Involving Risks to Subjects or Others (UPIRSOs), including adverse events, are not anticipated. In the unlikely event that such events occur, Reportable Events (which are events that are serious or life-threatening and unanticipated (or anticipated but occurring with a greater frequency than expected) and possibly, probably, or definitely related) or Unanticipated Problems Involving Risks to Subjects or Others that may require a temporary or permanent interruption of study activities will be reported immediately (if possible), followed by a written report within 5 calendar days of the Principal Investigator becoming aware of the event to the IRB (using the appropriate forms from the website) and any appropriate funding and regulatory agencies. The investigator will apprise fellow investigators and study personnel of all UPIRSOs and adverse events that occur during the conduct of this research project through regular study meetings or via email as they are reviewed by the principal investigator. The protocol's research monitor(s), the PI's faculty supervisor, YSPH will be informed of any adverse events such as unanticipated reaction from the participants (e.g. suicidal ideation) within 5 days of the event becoming known to the principal investigator.

- d. For multi-site studies for which the Yale PI serves as the lead investigator:
 - i. How will adverse events and unanticipated problems involving risks to subjects or others be reported, reviewed and managed? N/A
 - ii. What provisions are in place for management of interim results? N/A
 - iii. What will the multi-site process be for protocol modifications? N/A

specifically to sexual minority women.

4. **Potential Benefits:** Identify any benefits that may be reasonably expected to result from the research, either to the participant(s) or to society at large. (*Payment of participants is not considered a benefit in this context of the risk benefit assessment.*)

Benefits to participants: All participants in the present study will be exposed to information about how minority stress can contribute to depression, alcohol abuse, and other stressors. Also, this study will potentially contribute to the development of an evidence-based psychosocial intervention targeted

Benefits to society: The mental and behavioral health disparities experienced by sexual minority women constitute a clear public health concern. Benefits to society in general are anticipated through the

dissemination of intervention findings. Results will better inform local and national public health agencies about potentially effective outreach and prevention strategies that can be delivered to gay, bisexual, and other women who have sex with women who also experience mental health problems, such as depression, suicidality, and alcohol abuse.

SECTION VIII: RESEARCH ALTERNATIVES AND ECONOMIC CONSIDERATIONS

Alternatives: What other alternatives, if any, are available to the study participants outside of the research?
 N/A

2. **Payments for Participation (Economic Considerations):** Describe payments that will be made to participants, if any, the amount and timing of payments, and the conditions for receiving this compensation (if applicable). If you plan to hold a drawing, be sure to include the following on any consent or recruitment materials mentioning the lottery: 1) the value of the prize; 2) the sponsor of the prize (this cannot be a federal funding source); 3) the odds of winning; and 4) that there are no restrictions to winning.

Phase 1: Participants will be paid \$50 for completing a Phase 1 interview. Participants who come in to the Esteem Research Lab but who are deemed ineligible to begin an interview will be compensated \$10 to cover their travel expenses.

Phase 2: Participants will be paid \$100 for providing their feedback and completing an interview with an ESTEEM lab clinical team member.

Phase 3: Participants will be paid at each study visit: \$25 at baseline, \$25 at 3 month follow-up, \$75 at 6 month follow-up, and \$10 for each therapy session. Additionally, as part of retention efforts, upon randomization, we will be providing all participants with an "EQuIP Swag Bag" that includes candy, safer sex supplies, and study-branded pens and stress balls in a tote bag. Participants who complete a follow-up qualitative interview about their experience in the study will receive a \$40 Amazon gift card.

3. **Costs for Participation (Economic Considerations):** Clearly describe the participant's costs associated with participation in the research, if any, and the interventions or procedures of the study that will be provided at no cost to participants.

Study participation will generate no cost for participants. The study treatment will be provided free of charge to all study participants.

NCT03721276

Title of Research Project: Project EQuIP: Empowering Queer Identities in Psychotherapy

SAP Date 10.7.2019

Statistical Analysis Plan

Feasibility and Acceptability

Feasibility was assessed in terms of treatment attendance. Acceptability was assessed in terms of responses to the quantitative exit survey that all participants completed at 6-month follow-up and the qualitative exit interview conducted with 20 randomly selected participants after 6-month follow-up. Qualitative exit interviews were transcribed verbatim, and the third and eighth authors served as coders and double-coded all transcripts. Thematic analysis was used to identify patterns of responses, and emergent codes were categorized into larger themes (Braun & Clarke, 2006).

Intervention Efficacy

We assessed intervention efficacy using an intent-to-treat analysis including all eligible cases (n = 60). First, to determine randomization effectiveness, differences in baseline demographic characteristics were assessed between the immediate intervention (n = 30) and waitlist control (n = 30) conditions using t tests for continuous measures and chi-square tests for categorical measures. Income and gender identity differed between conditions (p < .05), with the waitlist control group reporting higher income and having a larger proportion of cisgender women; thus, we included income and gender identity as covariates in subsequent analyses.

Dependent variables were assessed for normality using skewness and kurtosis thresholds of ± 2 (Field, 2013; George & Mallery, 2010). Suicidality and internalized stigma were found to be non-normal; we therefore log-transformed these variables for further statistical tests (reassessment of skewness and kurtosis after transformation showed normal distribution).

In a first set of analyses, we used linear mixed models with maximum likelihood estimation and a compound symmetry covariance structure (selected based on fit criteria, i.e., lowest Akaike information criterion [AIC]) to test the Condition x Time interaction for all intervention outcomes including mental and behavioral health (e.g., depression), minority stress processes (e.g., rejection sensitivity), and universal risk processes (e.g., emotion regulation). To do so, we limited the data to baseline (time = 0) and 3 months postbaseline assessment (time = 1) and examined the Condition x Time interaction effect of receiving immediate EQuIP (condition = 1) versus receiving the 3-month waitlist (condition = 0). Thus, the estimate of interest compared preintervention to immediate postwaitlist outcomes in the immediate intervention group to prewaitlist and immediate postwaitlist outcomes in the waitlist control group. Effect sizes (d) for linear mixed models were calculated as mean pre–post change in the immediate intervention group to the mean pre–post change in the waitlist control group, divided by the pooled baseline standard deviation (Morris, 2008).

In a second set of analyses, we examined the clinical significance of observed changes in those mental health outcome measures that possess established clinical cutoffs (i.e., CES-D, ODSIS, OASIS). To do so, we used generalized linear mixed models with a logit link and binomial distribution to examine the Condition x Time interaction effect predicting the odds of meeting or

exceeding the clinical cutoff among participants receiving immediate EQuIP (condition = 1) versus those receiving the 3-month waitlist (condition = 0). For interpretability, we report proportions of participants meeting or exceeding clinical cutoff by condition and time.

In a third set of analyses, we conducted a pooled analysis whereby data from all participants were pooled to examine change in outcome from immediate preintervention to postintervention using paired t tests (i.e., baseline to 3 months postbaseline for the immediate intervention group and 3-months postbaseline to 6-months postbaseline for the waitlist control group). Pooled analyses are useful in waitlist-controlled studies (where all participants ultimately receive treatment) to assess the pre–post effect of the intervention in a larger sample than the condition x time analyses allow. One participant assigned to the waitlist control group did not complete 3-month or 6-month assessments and was dropped from the pooled analysis (n = 59). Effect sizes (d) for pooled analyses were calculated as $\frac{2t}{\sqrt{df}}$.

Finally, we assessed the longer-term persistence of observed intervention effects by limiting analyses to immediate 3-months postbaseline (time = 1) and 6-months postbaseline (time = 2) among participants in the immediate intervention condition (condition = 1), the only participants to have completed assessments 3-months after receiving the intervention. Specifically, we examined the significance of changes between time points for all outcomes, including mental and behavioral health (e.g., depression), minority stress processes (e.g., rejection sensitivity), and universal processes (e.g., emotion regulation). Results were evaluated at p < .05.

References

Braun, V., & Clarke, V. (2006). Using thematic analysis in psychology. *Qualitative Research in Psychology*, *3*(2), 77-101.

Field, A. (2013). Discovering statistics using IBM SPSS statistics. SAGE.

George, D., & Mallery, P. (2010). SPSS for Windows step by step. A simple study guide and reference (10. Baskı). *GEN, Boston, MA: Pearson Education, Inc.*

Morris, S. B. (2008). Estimating effect sizes from pretest-posttest-control group designs. *Organizational Research Methods*, *11*(2), 364-386. https://doi.org/10.1177/1094428106291059

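### Fitting the Condition x Time mixed models by maximum likelihood with 60 people makes the interaction SE about 1.7% too small and adds about 0.4 percentage points to the 5% error rate

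*SAP*

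**What the plan says.** All of this is in the SAP under Intervention Efficacy.

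- **Model.** The first set of analyses uses "linear mixed models with maximum likelihood estimation and a compound symmetry covariance structure". The covariance structure was chosen by lowest AIC.
- **Target.** The models are there to "test the Condition x Time interaction for all intervention outcomes", covering mental and behavioral health, minority stress and universal risk processes.
- **Data.** The analysts "limited the data to baseline (time = 0) and 3 months postbaseline assessment (time = 1"), so each person contributes at most two values.
- **Sample.** It is an "intent-to-treat analysis including all eligible cases (n = 60"), split into "immediate intervention (n = 30) and waitlist control (n = 30) conditions".
- **Covariates.** After a baseline comparison, "we included income and gender identity as covariates in subsequent analyses".
- **Missing follow-up.** "One participant assigned to the waitlist control group did not complete 3-month or 6-month assessments".
- **Threshold.** "Results were evaluated at p < .05".

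The SAP does not mention REML, a degrees-of-freedom method, any other small-sample correction, or whether the interaction is tested against a z, t or likelihood-ratio reference.

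**The concern.** ML estimates variance components as if the fixed effects were known, so it divides by the number of people rather than by the residual degrees of freedom. In a large trial this does not matter. With 60 people the variance of change is underestimated by a visible, though small, amount. The test statistic is then slightly too large in absolute value, and p-values are slightly too small.

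Two features make this worth a line in the review. The bias runs in one direction, towards declaring a difference. It also applies to the linear mixed model for every outcome, each read against a fixed .05 line. A result just under that line might sit just over it with a properly scaled standard error.

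**Working it through.** **Inputs.** From the SAP: N = 60 (30 per arm), two waves, ML, compound symmetry, and a threshold of .05. Assumptions: the test is two-sided (the SAP does not say); income and gender identity enter as baseline main effects; follow-up is complete for the main calculation.

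**Step 1: reduce the model.** With two waves, compound symmetry and complete data, the Condition x Time coefficient is the difference between arms in mean change. Covariates that do not vary over time drop out of a within-person contrast. The test is therefore a two-sample comparison of change scores, with 60 - 2 = 58 degrees of freedom.

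**Step 2: standard error.** The unbiased variance of change divides the within-arm sum of squares by 58; ML divides it by 60.

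SE(ML) / SE(unbiased) = sqrt(58/60) = 0.983, so the SE is 1 - 0.983 = 0.017, or 1.7%, too small.

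With complete data the estimated difference itself is the same under ML and REML.

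**Step 3: actual size.** A test that rejects when |estimate / SE(ML)| exceeds a critical value c has

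size = 2 x P(T58 > 0.983 x c).

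REML in the same setting has size 2 x P(T58 > c).

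| Reference | c | 0.983 x c | Size, ML | Size, REML | Added by ML |
|---|---|---|---|---|---|
| t, 58 df | 2.002 | 1.968 | 5.38% | 5.00% | 0.38 |
| t, 60 df | 2.000 | 1.967 | 5.40% | 5.02% | 0.39 |
| t, 116 df | 1.981 | 1.947 | 5.63% | 5.24% | 0.40 |
| normal | 1.960 | 1.927 | 5.89% | 5.48% | 0.41 |

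(The last column is in percentage points, from unrounded sizes. The 116 df are 120 observations less four fixed effects.)

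An ML likelihood-ratio test against chi-square on 1 df gives 5.50%.

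**Step 4: split the worst case.** With a normal reference the excess over 5% is 5.89 - 5.00 = 0.89 points. Of this, 5.48 - 5.00 = 0.48 comes from the normal reference and 5.89 - 5.48 = 0.41 from ML.

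**Step 5: missing data and covariates.** With 59 complete pairs the sizes are 5.39% (t, 57 df) to 5.90% (normal). Simulation used 60,000 null datasets per setting, with both covariates and within-person correlation 0.5 or 0.7:

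- Complete data or one missing 3-month value: ML gave 5.4-5.5% (t) and 5.9% (normal).
- Six missing values: ML gave about 5.3-5.4% (t) and 5.8-5.9% (normal).
- REML with t on 58 df and complete data: 5.0-5.1%.

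**The case against.** The strongest reply is that this is immaterial. At any fixed reference ML adds only about 0.4 points, so with a t reference on 60 df it changes the verdict only for outcomes whose correct p-value lies between .050 and about .054. The protocol (Section V, on how the enrolment estimate was derived) describes Phase 3 as powered mainly for feasibility and acceptability, with efficacy preliminary. The SAP also tests every outcome at .05 with no stated multiplicity adjustment, which is a larger issue than 0.4 points per test. All of this stands, and it is why the point is graded minor.

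A second reply is that ML was needed for the AIC comparison. It was not: REML supports AIC when the models differ only in covariance structure and share the same fixed effects, which is the selection the SAP describes.

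A third is that the software may have applied a degrees-of-freedom correction. It may have, but the SAP does not say so. A t reference on 58 df still leaves 5.38%, because the ML standard error itself is too small; only a correction that also rescales the standard error would remove the rest.

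Three stronger readings are tempting and are not supported:

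- **That ML by itself drives the test to 5.9%.** More than half of that excess needs a normal reference, which the SAP never states.
- **That reported confidence intervals or effect sizes are wrong.** The SAP specifies no confidence intervals. Its d is the difference in mean change over the pooled baseline SD, so the model standard error does not enter it.
- **That the persistence analysis in the 30 immediate-intervention participants is affected.** The SAP names no model for that analysis.

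**Conclusion.** The concern holds as a small, one-directional error. ML makes the Condition x Time standard error about 1.7% too small and raises the two-sided type I error by about 0.4 percentage points, to about 5.4% with a t reference on 58 to 60 df. If a normal reference was used the size is about 5.9%, and switching to REML alone would bring it only to about 5.5%.

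This rests on a two-sided test, covariates entered as main effects, and nearly complete 3-month data; the simulations show little sensitivity to one or six missing values. It covers the linear mixed models only, not the logistic mixed models or the paired t tests. Clear results are not threatened. Only p-values very near .05 could change side.

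**What to change.** Estimate the linear mixed models by REML with Kenward-Roger or Satterthwaite degrees of freedom, and state in the SAP which method is used. Both parts are needed: REML corrects the standard error, and the finite-sample degrees of freedom correct the reference distribution. Keep ML for comparing models with different fixed effects, which the SAP does not describe doing.

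The SAP is written in the past tense and already reports findings from the data, so the change is a refit after the data were seen. It should be labelled as such, with the ML results kept alongside and any outcome whose p-value crosses .05 listed.

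The cost is a software option, one sentence in the SAP, a rerun of each linear mixed model, and slightly larger p-values. No new data are needed.

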☑ Through local NGO or other local contact	☐ Departmental/Center research boards	□ Newspape
☑ Table set-up / in-person recruitment of	☐ Snowball sampling	
public		
☐ Classroom recruitment	☑ Social Media (Twitter/Facebook):	

3. Targeted Enrollment: Give the number of participants:

a. Targeted for enrollment at Yale for this protocol

Phase 1: 20 sexual minority women **Phase 2:** 10 SMW experts **Phase 3:** 60 sexual minority women b. If this is a multi-site study, give the total number of participants targeted across all sites N/A

4. How was this estimate derived?

 \square Other:

For both Phase 1 and Phase 2, estimates were derived based on the number of interviews required to reach saturation in previous intervention development studies. For Phase 3, this part of the study is powered primarily to examine feasibility and acceptability. This phase will also allow us to determine the preliminary efficacy of the intervention. We will use Cohen's d and Hedge's g corrected for sample size, both of which express the average amount of individual change between intervention and control groups in terms of units of standard deviation. Group means on continuous variables typically begin to stabilize by 20-30 participants, and our waitlist design enables us to estimate effect sizes both by comparing intervention and control conditions at 3-months (n = 30/condition) and by examining pre-post effect sizes for the entire sample (n = 60). Our sample size provides sufficient power (1 - β =.8) to detect

intervention effects consistent with effect size estimates identified in our intervention research with sexual minority men in which the relative reduction in depression was 0.55 between intervention and control groups.

5. Process of Consent/Assent (NOTE: When a study includes minors, parent provide permission [not consent] for the child's participation, and the child provides assent for participation)

Describe the setting and conditions under which consent/assent will be obtained, including parental permission or surrogate permission and the steps taken to ensure participants' independent decision-making.

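### The randomised 3-month contrast is a difference in mean change without adjustment for baseline score: valid, but usually less precise than it could be from data already collected

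*SAP*

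**What the plan says.** The first set of analyses under Intervention Efficacy in the SAP is the only randomised comparison of the continuous outcomes. Its data are two waves: "we limited the data to baseline (time = 0) and 3 months postbaseline assessment (time = 1". The model is a linear mixed model fitted by maximum likelihood with a "compound symmetry covariance structure (selected based on fit criteria, i.e., lowest Akaike information criterion [AIC"), and the quantity tested is Condition x Time. The effect size is also change-based: "Effect sizes (d) for linear mixed models were calculated as mean pre–post change in the immediate intervention group", set against the same change in the waitlist arm and scaled by the pooled baseline SD.

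Two covariates enter. The SAP reports that "Income and gender identity differed between conditions (p < .05") and continues: "thus, we included income and gender identity as covariates in subsequent analyses". Nowhere does it list the baseline value of the outcome as a covariate or say that baseline means are held equal across arms.

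The analysis set is an "intent-to-treat analysis including all eligible cases (n = 60"). Under the pooled analysis the SAP adds: "One participant assigned to the waitlist control group did not complete 3-month or 6-month assessments". The 3-month comparison therefore has 30 v 29 complete pairs.

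In the protocol's account of how enrolment was derived (Section V, item 4), Phase 3 is described thus: "this part of the study is powered primarily to examine feasibility and acceptability". Preliminary efficacy is a further aim, with 80% power claimed for an effect of 0.55.

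**The concern.** Having the baseline rows in the model looks like baseline adjustment, but it is not. With two waves, a condition effect and free baseline means, the interaction is one arm's mean change minus the other's. That subtracts the whole baseline score (slope 1), whereas the data usually support a slope below 1, so baseline noise enters the contrast.

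Income and gender identity do not fill the gap. Entered as main effects they are constant over time and cancel out of the interaction.

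At stake is the width of the interval around the preliminary efficacy estimate. With 30 per arm that interval is wide, and the baseline scores that could narrow it are already in hand.

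**Working it through.** **Inputs.** From the documents: 30 v 30 randomised, one waitlist participant without a 3-month value, threshold p < .05, effect 0.55 (read as SD units). Assumed, because the documents do not give them: the correlation r between baseline and 3-month score, equal SDs unless stated, and a two-sided test.

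**The plan's own figure.** Comparing 3-month means at 30 per arm with SD 1, SE = sqrt(2/30) = 0.258. Then 0.55/0.258 − 1.96 = 0.17, so power is 0.57 (0.55 with the t distribution), not 0.80. With 30 v 29, power of 0.80 needs r of about 0.73 for the change test or 0.68 with baseline adjustment. This mismatch is a separate matter; here it shows only how much depends on the unstated r.

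**Is the coefficient a change difference?** The SAP's model was fitted to one simulated complete data set. The interaction was −0.6745 and the raw difference in mean change was −0.6745; adding the two covariates as main effects left it at −0.6745. In a second data set with one 3-month value missing, the figures were −0.574 and −0.584. So yes, nearly so with the missing value.

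**Is it valid?** In 20,000 simulated trials per setting, both the change test and ANCOVA were unbiased, with type I error 0.048 to 0.052.

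**Precision, equal SDs.** In SD units, with c = 1/30 + 1/29 (sqrt(c) = 0.2604) and N = 59:

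- change: variance = 2(1 − r)c
- baseline-only ANCOVA: variance = (1 − r²)c(1 + 1/(N − 4))
- ratio = (1 + r)/2 × (1 + 1/55)

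Half-widths use t = 2.002 (57 df) and 2.003 (56 df). At r = 0.5, for example, 2.002 × 0.2604 = 0.521, and 2.003 × 0.2604 × sqrt(0.764) = 0.456.

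| r | variance ratio | fall | half-width, change | half-width, adjusted |
|---|---|---|---|---|
| 0.3 | 0.662 | 34% | 0.617 | 0.502 |
| 0.5 | 0.764 | 24% | 0.521 | 0.456 |
| 0.7 | 0.865 | 13% | 0.404 | 0.376 |
| 0.8 | 0.916 | 8% | 0.330 | 0.316 |
| 0.9 | 0.967 | 3% | 0.233 | 0.229 |

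Simulation (200,000 trials per r) gave ratios of 0.660, 0.765, 0.867, 0.916 and 0.970.

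**Unequal SDs.** With k = follow-up SD / baseline SD, the fall is 1 − (1 + 1/55)(1 − (1 − rk)²/(1 + k² − 2rk)). At k = 1.2 it is 1.6% at r = 0.7, and a 1.5% loss at r = 0.8. If an unstructured covariance was among the AIC candidates (the SAP does not list them), choosing compound symmetry would limit k to about 0.85–1.17, 0.88–1.14 and 0.90–1.12 at r = 0.5, 0.7 and 0.8. The falls would then be 13–37%, 4–26% and 1–20%.

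**ANCOVA that also carries the two covariates.** Both differ between arms, so they inflate the variance of the treatment effect. At exactly p = .05 with n = 60, R² with condition is 0.065 (income) and 0.064 (gender identity, taken as binary). If the two are uncorrelated, inflation is 1/(1 − 0.129) = 1.148. If they also predict nothing beyond baseline, the ratio is (1 + r)/2 × 1.148 × (1 + 1/53) = 0.760, 0.877, 0.994, 1.05 and 1.11 at r = 0.3, 0.5, 0.7, 0.8 and 0.9. It reaches 1 near r = 0.71.

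**Common-baseline mixed model.** With the covariance taken as known and the covariates as main effects, the ratio to the SAP's model is about 0.78, 0.87 and 0.91 at r = 0.5, 0.7 and 0.8, before small-sample cost.

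**The case against.** The strongest reply is that nothing here is an error. Both estimators are unbiased, and the choice is consistent: the protocol's planned effect sizes are themselves framed as average individual change, and the SAP delivers that with a cited pretest-posttest-control formula. This stands as far as it goes. But under randomisation the adjusted analysis targets the same difference, so a usually narrower interval comes at almost no cost.

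Second, the benefit rests on r and SDs that the documents do not report, and it can vanish. This stands, and it is why only a range is given.

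Third, power gains (for example 0.55 to 0.66 at r = 0.5) cannot be realised: the SAP is written with results known, and the fix keeps Condition x Time as the only test. This also stands. Power is illustrative; the benefit is interval width.

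Fourth, if the common-baseline model let covariate effects vary over time, its variance relative to the SAP's main-effects model would be about 0.87, 0.98 and 1.04 at r = 0.5, 0.7 and 0.8. That compares unlike models. With those terms in both, the common-baseline model again cuts variance by about 25%, 15% and 10%. It does show that the covariate specification must be stated.

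A reader might go further and infer that the reported effects are biased, or distorted by a baseline gap in the outcomes. The documents do not support this. The contrast is unbiased over randomisations, and the SAP reports imbalance only in income and gender identity, not in any outcome.

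**Conclusion.** The point holds as a matter of efficiency. As described, the randomised contrast on continuous outcomes leaves the outcome's baseline score unadjusted. With equal SDs and r between 0.3 and 0.9, adjustment would lower its variance by 34% down to 3%. The gain is worthwhile at moderate r, and small or slightly negative at high r or when the SD rises at follow-up.

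This rests on three things: an assumed r; a reading of the model with free baseline means and main-effect covariates, which the stated estimate and effect size imply but no printed formula confirms; and 30 v 29 complete pairs. Had the condition main effect been left out, precision would already be near that of ANCOVA, but the text does not describe that model.

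It would be wrong to infer that the test is invalid, that any reported conclusion would change, or that adjustment would make good the stated 80% power. Neither document names a primary outcome or analysis, and Phase 3 is sized mainly for feasibility and acceptability. This is a recommended improvement, not a defect that undermines the trial.

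**What to change.** For each continuous outcome, report beside the Condition x Time result the baseline-adjusted 3-month difference with its 95% CI.

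- **Preferred model:** a two-wave mixed model with a common baseline mean across arms, unstructured 2x2 covariance, REML with the Kenward-Roger correction, and income and gender identity as main effects, as the SAP's own model is read here. It keeps all 60 participants, in line with the intent-to-treat statement.
- **Alternative:** ANCOVA of the 3-month score on condition and baseline score, stating that it uses n = 59. In four simulated data sets at r = 0.5, a common-baseline model gave the same estimate to four decimals, so the choice concerns who is included more than the answer.
- **Sensitivity only:** ANCOVA that also includes income and gender identity, noting that it may gain nothing above r of about 0.7.

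Use the log scale at both times for suicidality and internalized stigma. Base the accompanying d on the adjusted difference over the pooled baseline SD. Print the model formula, including how the covariates enter, and report the observed r and SDs so that readers can judge the gain.

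Label the result a re-analysis made with results known, keep Condition x Time as the reported test, and make no second significance claim.

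The cost is one extra model per outcome and a second effect-size column, with no new data or visits. The downside is a second, post-results estimate for each outcome, which the labelling is there to contain.
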